## Background

Gestational diabetes mellitus (GDM), a complication of glucose intolerance with first recognition in pregnancy, is one of the most common medical problems in pregnancy and strongly linked with the development of type 2 diabetes (T2D) later in life (1–3). Thirty percent of women with GDM will have persistent postpartum dysglycemia, and up to 70% ultimately receive the diagnosis of T2D within 10 years postpartum (4,5). Therefore, postpartum blood glucose screening is important to detect prediabetes and T2D, allowing timely treatment (3-7). For this reason, both the American Diabetes Association (ADA) and American College of Obstetrics & Gynecology (ACOG) recommend a 2-h 75-gram oral glucose tolerance test (OGTT) for all women who had GDM 6–12 weeks after delivery to detect persisting glucose intolerance or diabetes mellitus after pregnancy (8).

Unlike other laboratory tests performed, the OGTT involves several phases, including the need to fast for several hours, to drink a concentrated glucose solution which can induce unpleasant gastrointestinal effects, the collection of three to four blood samples, and the need to remain seated in the laboratory for two to three hours (9). Ingestion of the glucose solution is an important cause of discomfort for patients undergoing an OGTT. Less than half of the women who had GDM comply to the recommendations of postpartum 75-gram OGTT diabetes screening and the majority do not attend any screening for T2D postpartum (10-12). The average compliance rate for postpartum OGTT testing is 35%, largely related to women perceiving the test as inconvenient (13-15). For example, in England, a study which examined postpartum glucose screening rates in women with a history of GDM, using a nationally representative sample from 127 urban and suburban primary care practices, found that just 18.5% of women had glucose screening within six months of birth [16]. Additional studies have identified reasons for non-attendance or non-completion from the perspective of women (17-19); these reasons included: time pressures, lost laboratory forms, not knowing a test was necessary (15,19) feelings of emotional stress while adjusting to a new baby and fear of a T2D diagnosis [(17-19).

The recommended diabetes screening test postpartum is the OGTT, as hemoglobin A1c (HbA1c) is less sensitive to the rapid glycemic variations and

blood volume changes expected after a recent GDM pregnancy. HbA1c reflects average glycemic exposure over the preceding 2–3 months and is commonly used in people with diabetes to monitor long-term (~3 months) glycemic control (20). Even though the HbA1c is faster, easier, and less expensive to administer, it results in false negative findings 60–70% of the time when the OGTT detects diabetes (21,22). While chronic blood glucose concentrations influence HbA1c levels, many other factors can increase or decrease HbA1c as well, which could lead to questionable HbA1c results and poor alignment with the OGTT. HbA1c levels can be affected by genetic, hematologic, and illness-related factors, especially anemia (23).

Interestingly, the ADA has acknowledged that in patients in whom HbA1c is unreliable (especially those with hemoglobinopathies, altered red cell turnover or impaired renal function), the assessment of other indices of chronic glycemia may be advisable, although their relation with average glucose and prognosis remains uncertain (24). HbA1c reflects the glucose concentration during the entire lifespan of the red blood cells but to the largest extent the 6–8 weeks preceding the time of measurement (20). Certain factors, e.g. red blood cell disorders, could potentially bias the measurement of HbA1c and therefore alternative markers could be useful (24, 25). One such marker is fructosamine which relates to average levels of glucose during the preceding 1 to 3 weeks (24,25). Fructosamine may give an earlier indication of poorly controlled glucose compared to HbA1c. It is a simple, robust and inexpensive biomarker that could potentially be a useful tool in large epidemiological and clinical studies either as a stand-alone indicator of hyperglycemia or in combination with glucose and HbA1c (25). Importantly, fructosamine may be reliably measured irrespective of fasting or non-fasting. Glycated albumin is the percentage of serum albumin to which a glucose molecule has been nonenzymatically attached, while fructosamine refers to all ketoamine linkages resulting from serum protein glycation (26). The term “fructosamine,” therefore, typically refers to all ketoamine linkages that result from glycation of serum proteins. In non-pregnant populations, fructosamine has been shown to adequately identify individuals with diabetes, and to improve diabetes detection when used in combination with HbA1c or fasting glucose (27). Glycated serum proteins, such as fructosamine, may avoid issues related to

RBC turnover and provide viable alternatives to HbA1c as a marker of glycemia. In particular, these biomarkers are not based on hemoglobin and hence, do not depend on RBC turnover (26). Since fructosamine reflects the average levels of blood glucose during the former 1 to 3 weeks, fructosamine also mirrors a poorly controlled glucose metabolism better than HbA1c (27). However, some physiological and pathological conditions can significantly influence the metabolism of fructosamine. In brief, all those clinical conditions that affect protein metabolism potentially influence the concentrations of glycosylated proteins (28). Thus, physiologic or pathologic conditions linked to hypo-proteinemia (i.e., pregnancy or malnutrition) are more likely to affect the concentration of fructosamine. Another disadvantage of fructosamine is that its concentration is considerably influenced by the levels of immunoglobulins, especially IgA, which are present in abnormal concentration in a broad range of clinical conditions.(29).

Among women who experience glucose abnormalities during pregnancy, screening during the postpartum period offers a window of opportunity for early identification of diabetes and prediabetes. The rates of postpartum T2D screening with an OGTT for women with GDM are not optimal given the majority of women with GDM fail to return for postpartum glucose testing. A new device called a continuous glucose monitor or “CGM” is a small disc that is placed on the arm and can be easily placed and removed by the person wearing it. It is worn for 10 days and can stay in place for activities such as sleeping and showering. Over 10 days, over 1000 sugar measurements are taken without the person wearing the device having to do any testing (30). Continuous glucose monitoring (CGM) systems have been recognized as an ideal method of monitoring glycemic control in diabetic patients (30,31). The data of rigorous 24 h glucose profiles from CGM allow the calculation of glycemic variations, detection of asymptomatic hypoglycaemia and accurately depict the characteristics of blood glucose fluctuations (30,31). In the past decade, CGM has been proven to have similar accuracy to self-monitoring of blood glucose (SMBG) and yet provides better therapy optimization and detects trends in glucose values due to higher frequency of testing. Although CGM has been used successfully in T1D and T2D patients (31), the effectiveness of CGM in improving pregnancy outcomes

complicated by GDM is still understudied (32). Current updated evidence suggests that CGM is superior to SMBG among GDM pregnancies in terms of detecting hypoglycemic and hyperglycemic episodes, which might result in an improvement of maternal and fetal outcomes (33). In addition, CGM is effective at capturing gestational glucose profiles and improving treatment effect among pregnant women with GDM (34,35). Further research is needed to explore the clinical utility such screening and predictive values of CGM for glucose impairment after having diabetes during pregnancy. We need to improve diabetes testing after childbirth in women who experienced gestational diabetes. This will allow us to target our efforts to improve the early diagnosis and treatment of diabetes following GDM. No studies conducted to date have not comprehensively examined whether CGM after delivery can be used in women with a recent history to predict their risk of diabetes.

#### STUDY OBJECTIVE

Given the damaging effect of prolonged undetected hyperglycemia, prevention and early diagnosis of T2D is cost-saving and of public health importance. This research study is being done to assess if using a glucose sensor (also known as a continuous glucose monitor or CGM) after childbirth can help identify women who are at risk of developing diabetes after having diabetes during pregnancy or gestational diabetes. Currently, screening for diabetes after childbirth is performed with an oral glucose tolerance test 4-16 weeks after delivery, but this is burdensome and most patients are non-compliant. This study will use a CGM worn on the skin for 10 days. The data from the sensor will be compared to the standard oral glucose tolerance test as well as a HbA1c and fructosamine test. This is a single site study from patients with recent GDM that attended the diabetes clinic at Woman's Hospital. The research team plans to enroll 50 participants aged 18 years or older into the study. Participation in the study is expected to last up to 10 days during the postpartum interval. Study procedures include; 1) consent and screening; and 2) sensor placement and download after 10 days of wear postpartum during which an OGTT, fructosamine and HbA1c test will be administered.

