## STUDY PLANS AND PROCEDURES

### Participants and Treatment Regimen

This is a prospective observational study of fifty postpartum women with a recent GDM pregnancy. All participants will be requested to return at 4-16 weeks postpartum for a 75 gm 2-hour OGTT as part of standard care after gestational diabetes. Fifty women with a history of GDM will be enrolled to use a blinded continuous glucose monitor (Dexcom G7). All CGM data will be masked and therefore not available to participants, clinicians, or researchers in real time. Participants otherwise will receive standard clinical care. All participants will be recruited from the Woman's Hospital Diabetes Clinic or from the maternal fetal medicine practice referring to the clinic. Those who wish to participate will provide written informed consent. The Woman's Hospital Institutional Review Board (WHIRB) will have approved both the protocol and consent.

All subjects will undergo a verbal screen, and if they are eligible and sign a medical release form, their medical records will be obtained to confirm their medical history. After consenting, demographic data, gravidity, parity, and body mass index (BMI) will be obtained. The patient's physician will be notified of participation in the study and have access to the laboratory results.

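### The objective and rationale are worded as prediction of future diabetes, but the design can address only concurrent OGTT status

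*Combined protocol and SAP*

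**What the plan says.** The Study Objective section gives the aim as assessing whether a glucose sensor worn after childbirth "can help identify women who are at risk of developing diabetes after having diabetes during pregnancy or gestational diabetes". The Background describes as unexamined "whether CGM after delivery can be used in women with a recent history to predict their risk of diabetes".

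The procedures are short and concurrent. "Participation in the study is expected to last up to 10 days during the postpartum interval". The second of the two listed procedures is "sensor placement and download after 10 days of wear postpartum during which an OGTT, fructosamine and HbA1c test will be administered". The comparison is stated directly: "The data from the sensor will be compared to the standard oral glucose tolerance test as well as a HbA1c and fructosamine test".

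The section on HbA1c, fructosamine and OGTT data sorts women into normal, prediabetes or diabetes from these tests. Under Participants and Treatment Regimen, medical records are obtained to confirm history, with no mention of later review. The Statistical analysis section lists Pearson correlation, chi-square, t, Mann-Whitney and Kruskal-Wallis tests. It contains no longitudinal or prediction analysis, and no sensitivity, specificity, ROC or agreement analysis.

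**The concern.** The words used for the aim and the gap refer to a future state. Every measurement refers to the present. Each woman's reference status is recorded once, so no change from non-diabetic to diabetic can be observed.

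What is at stake is the conclusion. The objective governs what a significant correlation or group difference will be taken to show. Under the present wording, agreement between CGM and the OGTT on one occasion could be read as evidence that CGM predicts diabetes. Nothing in the plan limits the conclusion to current status.

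**Working it through.** **Plan's own figure.** The only relevant figure is the sample size of 50. It comes with no effect size, power, precision target or dropout allowance, so there is nothing to reproduce.

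**Step 1. Question against data.**

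| Element | Stated question | What is collected |
|---|---|---|
| Outcome | Risk of developing diabetes | Normal, prediabetes or diabetes on current tests |
| Timing | After the postpartum period | Within the 10-day sensor wear |
| Follow-up | Needed | None described |
| Analysis | Prediction of a later event | Correlations and group tests |

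The design is labelled prospective: "This is a prospective observational study of fifty postpartum women with a recent GDM pregnancy". Here that describes how the data are gathered; it supplies no follow-up. The table of contents lists Duration of Study and Outcome Measures, but the text available has no sections under those headings. Nothing elsewhere indicates longer observation.

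**Step 2. Can current OGTT status stand in for future diabetes?** The inputs are from the Background: 30% persistent postpartum dysglycemia, and up to 70% type 2 diabetes within 10 years.

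- Dysglycemic now: 0.30 × 50 = 15.
- Later diabetes at the upper figure: 0.70 × 50 = 35.
- If all 15 are among the 35, then 35 − 15 = 20 future cases (20/35 = 57%) are not dysglycemic at this visit.
- At an assumed 10-year incidence of 50%: 25 − 15 = 10 of 25 (40%).
- At an assumed 30%: 15 − 15 = 0.

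These are minimum counts, because they assume that every currently dysglycemic woman goes on to diabetes. At the upper figure, a CGM metric that matched the OGTT perfectly would still miss more than half of later cases. The two questions coincide only if long-term incidence is close to current prevalence.

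**Step 3. What the concurrent question can deliver.** Assume that 30% prevalence applies to this clinic and that all 50 women complete the OGTT. That gives 15 affected and 50 − 15 = 35 unaffected. The exact (Clopper-Pearson) 95% interval for x of n runs from the 2.5% point of Beta(x, n − x + 1) to the 97.5% point of Beta(x + 1, n − x). When x = n the upper limit is 100%.

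| Illustrative result | Estimate | Exact 95% interval |
|---|---|---|
| Sensitivity 9/15 | 60% | 32% to 84% |
| Sensitivity 12/15 | 80% | 52% to 96% |
| Sensitivity 15/15 | 100% | 78% to 100% |
| Specificity 28/35 | 80% | 63% to 92% |
| Specificity 32/35 | 91% | 77% to 98% |

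Concurrent accuracy can be estimated, though loosely. Future risk cannot be estimated from the planned data.

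**The case against.** The strongest reply is that one clause has been read apart from its surroundings. The Study Objective section opens with early diagnosis, describes the OGTT as the current and burdensome screening test, and then says that sensor data will be compared with it. The Background speaks of improving testing after childbirth and of identifying diabetes and prediabetes early. On that reading, a woman at risk is one with an abnormal OGTT now, and CGM is being tried as an easier screening test. The text also says only that the study will assess whether CGM can help, and it plans no prediction model.

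Much of this stands. The looser reading is plausible, and under it the fault is one of wording, which lowers the severity. It does not remove the fault, because the Background asks whether CGM "can be used in women with a recent history to predict their risk of diabetes", and nothing confines the conclusion to current status.

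A reader might also want to express the problem as expected incident cases. With a constant hazard (an assumption) fitted to the upper figure, h = −ln(0.30)/10 = 0.120 per year, and 50 × (1 − exp(−0.120 × 10/365.25)) = 0.16 cases in 10 days. At assumed 10-year incidences of 20% to 50%, the result is 0.03 to 0.10. The arithmetic is sound, but the plan never sets out to count new cases over 10 days. The figure only restates that there is no follow-up, and it does not measure the size of the problem.

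**Conclusion.** The point holds at moderate severity. The aim and rationale are phrased as prediction, while the design supports a statement only about concurrent OGTT-defined dysglycemia. This rests on the text alone and needs no numerical assumption.

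The figures in Steps 2 and 3 do rest on assumptions: that the Background's 30% and upper-limit 70% apply to this clinic, and that all 50 women complete the OGTT. Fewer completers would widen the intervals.

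Two stronger readings are not supported. A reader might infer that the study cannot answer anything useful; in fact the comparison with the OGTT is stated and can be analysed. A reader might infer that the sponsor commits to reporting prediction; the plan contains no such commitment, and that outcome is a risk created by the wording.

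**What to change.** 1. **Study Objective.** Restate the aim along these lines: *to estimate how well 10-day CGM metrics identify concurrent prediabetes or diabetes on the 75 g OGTT at the postpartum visit*. Add that no conclusion about future diabetes will be drawn.
2. **Background.** Keep the remark on missing prediction studies as a comment on the literature if wished, but do not present this study as filling that gap.
3. **Statistical analysis.** Add the analysis that the new objective needs: ROC area, and sensitivity and specificity of named CGM metrics against OGTT status, with exact 95% intervals. State in advance which metrics are used and how any cut-off is chosen. The OGTT categories also need reconciling before they serve as the reference, because a fasting value of 100 to 125 mg/dl meets the protocol's wording for both normal and prediabetes.

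If the sponsor prefers to keep the predictive aim, the alternative is later follow-up with an incident-diabetes outcome and a matching analysis. That is a different and larger study.

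**Cost of the recommended route.** No new visits or data. The price is a narrower claim, some added analysis work, and intervals as wide as those in Step 3, which the report should acknowledge.

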##### **Exclusion criteria:**

- pregestational diabetes (type 1 or type 2)
- include known known skin adhesive allergy which would prevent subject from wearing a CGM,
- history of bariatric surgery or other surgeries that induce malabsorption
- long-term use (>2 weeks) of systemic steroids during the testing interval
- inability or refusal to comply with protocol

For study participants, a Dexcom G7 CGM (Dexcom, Inc., San Diego, CA, United States) in blinded mode (participant unable to see the glucose values) will be worn for 10 days. Dexcom G7 CGM sensor measures interstitial glucose concentrations every 5 minutes. Insertion of the sensor will require an additional hospital visit for DEXCOM placement and women will be offered flexibility in scheduling to assist compliance. Trained research personnel will assist in implanting the sensors. Neither participants nor professionals will have access to the glucose measurements during sensor use. The Dexcom G7 sensors will be removed after 10 days and returned to study coordinator. All participants will receive a \$100 incentive for participation in the trial

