#### HbA1c, Fructosamine and OGTT data

We will use the glucose levels and HbA1c values as defined by the American Diabetes Association (ADA) guidelines(8) for the diagnosis of normal, prediabetes, and type 2 diabetes. Following the guidelines of ADA, a fasting blood glucose (FBG) below 126 or 2-h blood glucose (2hBG) < 140 mg/dl is considered normal glucose tolerance; FBG of 100-125 mg/dl or 2-h blood glucose (2hBG)  $\geq$  140- 199 mg/dl is classified as prediabetes, and FBG above or equal to 126 mg/dL or 2-h blood glucose (2hBG)  $\geq$  200 mg/dl in a standard oral glucose tolerance test (OGTT) as diabetic. The reference ranges for HbA1c results are:

- No diabetes: below 5.7%
- Borderline/prediabetes: 5.7% to 6.4%
- Diabetes: 6.5% or higher (8)

Fructosamine results may be considered alongside the HbA1c and other tests.

- In non-diabetics with normal albumin, fructosamine levels normally range between 175-265umol/L (micromoles per liter). For people with uncontrolled diabetes, the fructosamine range is 268-870 millimoles per liter (mmol/L). The concentrations of fructosamine corresponding prediabetes and diabetes clinical cut-points of 5.7% and 6.5% for HbA1c, based on percentiles, were 241.4 umol/L (the 77.1 percentile) and 270.2 umol/L (the 96.5 percentile), respectively (36).

Collection of glucose data The blinded glucose monitoring data on glycemia will be retrospectively assessed. The participant data collected from the CGM (Dexcom G7) will be downloaded with the Dexcom G7 reader and uploaded to Dexcom CLARITY

The percentage of time-in-target range, time hypoglycemia, and time hyperglycemia will be reported as either means with standard deviations (SD) or medians with interquartile ranges (IQR), depending on variable distribution. For analyses assessing overnight glycemia, daytime is defined as 5:00 AM to 11:59 PM and nighttime as 12:00 midnight to 4:59 AM

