#### Statistical analysis

Statistical analyses will be performed using SPSS version 15.1 for Windows (SPSS, Inc.; Chicago, IL). Continuous variables will be tested for normality of distribution using the Kolmogorov-Smirnov test. When necessary, non-normally distributed data will be subjected to logarithmic or square-root transformation to obtain a normal distribution where necessary for subsequent analyses. Continuous parameters will be given as means  $\pm$  standard deviations or medians with interquartile ranges (IQR). Results will be presented as mean  $\pm$  standard deviation for normally distributed continuous variables and as medians, with the 25th and 75th IQR for non-normally distributed variables. Categorical data will be presented as percentage. Pearson correlation coefficient ( $r$ ) and the significance for it ( $p$ ) will be calculated between the variables. The chi square test will be used to compare categorical variables. Chi-square test will be used to test differences in percentage proportionality Student t tests will be used to compare normally distributed groups; otherwise, Mann-Whitney rank sum tests will be used. Multiple groups will be compared using Kruskal-Wallis one-way ANOVA with a Dunn's test for pairwise comparisons when appropriate. A two-sided P-value  $< 0.05$  is considered statistically significant.

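### If time in hyperglycemia is compared with the OGTT, the CGM figure includes the response to the OGTT's own glucose load; the effect is small unless free-living time high is low

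*Combined protocol and SAP*

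**What the plan says.** The Study Objective section describes the second procedure as "sensor placement and download after 10 days of wear postpartum during which an OGTT, fructosamine and HbA1c test will be administered". The same section states the comparison: "The data from the sensor will be compared to the standard oral glucose tolerance test", with HbA1c and fructosamine as further comparators. Under Participants and Treatment Regimen the test is a standard-care 75 g load: "All participants will be requested to return at 4-16 weeks postpartum for a 75 gm 2-hour OGTT".

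The paragraph after the exclusion criteria gives the sampling rate: "Dexcom G7 CGM sensor measures interstitial glucose concentrations every 5 minutes". The section on HbA1c, fructosamine and OGTT data names the CGM measures: "The percentage of time-in-target range, time hypoglycemia, and time hyperglycemia will be reported". It gives no glucose cut-offs for them and no excluded period. Its only rule about time of day is that "daytime is defined as 5:00 AM to 11:59 PM and nighttime as 12:00 midnight to 4:59 AM". The same section uses the 2-hour glucose, with the fasting value, to class women as normal, prediabetic or diabetic.

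The Statistical analysis section says that a Pearson correlation "will be calculated between the variables", without naming them. It also provides for transformation of skewed data and for group comparisons, at two-sided 0.05. It adds no rule on readings from the OGTT day.

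**The concern.** The study asks whether CGM can identify women at risk because the OGTT is burdensome. A woman screened by CGM alone would have no 75 g load on her trace. Here she would, and the height and length of that excursion are closely tied to the 2-hour value against which the CGM is judged. A woman with a high 2-hour glucose gains minutes above threshold from the test itself, whatever her glucose does on the other days. Part of any correlation, or of any difference between OGTT classes, would then be built in, and it would favor the result the study hopes to find.

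The point is conditional. The plan does not say which CGM variable is paired with which OGTT result. It applies if time in hyperglycemia, one of the three CGM measures the plan names, is among them.

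**Working it through.** The plan gives no figure for this overlap, so there is none to reproduce.

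**Arithmetic from the design**

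- Readings per full wear: 10 days × 24 h × 12 per hour = 2,880.
- 2-hour test: 24 / 2,880 = 0.83%. 3 hours: 36 / 2,880 = 1.25%. These are the ceilings, in percentage points, on what the load can add to time in hyperglycemia.
- Each load-induced hour above threshold: 12 / 2,880 = 0.42 points.
- Daytime period (19 h): 19 × 12 × 10 = 2,280 readings. One hour adds 12 / 2,280 = 0.53 points; 3 hours is 36 / 2,280 = 1.58%.

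**Relative size**

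Let b be the free-living proportion of time high (assumed) and m the minutes above threshold in the 3 hours after the load (assumed). The wear lasts 14,400 minutes, so the full-trace value is [b × (14,400 − 180) + m] / 14,400. With m = 60:

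- b = 1%: (142.2 + 60) / 14,400 = 1.40%, a relative rise of 40%
- b = 5%: (711 + 60) / 14,400 = 5.35%, a rise of 7%
- b = 10%: (1,422 + 60) / 14,400 = 10.29%, a rise of 3%

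**Induced association**

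The documents give no threshold, baseline or curve shape, so every input here is an assumption:

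- n = 50, and free-living time high is independent of the OGTT.
- 2-hour glucose is normal with mean 120 and SD 32 mg/dl, which puts about 27% of women at 140 or above.
- Free-living time high is lognormal with SD equal to its median.
- Fasting glucose is normal (90, 8). The peak at 45 minutes is the 2-hour value + 30 + N(0, 15). Glucose then falls linearly to the 2-hour value at 120 minutes and halfway back to fasting at 180 minutes.

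Under this curve the mean time above threshold after the load is about 9 minutes at 180 mg/dl and about 51 minutes at 140 mg/dl. At n = 50, significance needs |r| of about 0.28. Rejection rates for the Pearson test, raw to log scale, nominal 5%:

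| Threshold | Median free-living time high | Rejection |
|---|---|---|
| 180 mg/dl | 1% | about 12-15% |
| 180 mg/dl | 2% | about 7-8% |
| 180 mg/dl | 3% | about 6% |
| 140 mg/dl | 3% | about 13-22% |
| 140 mg/dl | 5% | about 9-13% |
| 140 mg/dl | 10% | about 6-7% |

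Repeat runs with other seeds move these by up to about two percentage points. Mean induced r (raw/log) is 0.11/0.14 at 180 mg/dl with a 1% baseline, and 0.12/0.18 at 140 mg/dl with 3%. With the 3 hours after the load excluded, r is 0.00 and rejection about 5%.

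Mean glucose, under similar assumptions (free-living SD 6-12 mg/dl), gives r of 0.01-0.05 and rejection of 5-6%, so it is not materially affected.

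**The case against.** **Timing.** Only the Study Objective section puts the OGTT inside the wear. Elsewhere the OGTT is standard care at 4-16 weeks and sensor placement is an additional visit, with no day fixed relative to the test. An OGTT before placement or after removal would add no readings. That is true, but the Study Objective is the only text that relates the two in time, and it places the test during the wear. Under an exclusion rule, a test outside the wear simply loses nothing.

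**Pairing.** The plan promises to report time in hyperglycemia and does not promise to correlate it with the OGTT. This stands, and it is why the point is conditional.

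**Size.** A reader might infer that the overlap by itself could make about half of null studies, or more, significant. Figures of that order can be produced, but only by joining about an hour of load-induced time high, which fits a threshold near 140 mg/dl, to a 1% free-living baseline, which fits a higher threshold. Lowering the threshold also raises the free-living baseline. The documents state neither value, so they do not support that combination.

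**Realism.** No true relation is a stress case, since the Background expects 30% of women to have persistent dysglycemia. Suppose the true raw r is 0.27. Over four assumed excursion patterns the observed raw r is 0.31-0.36 at a 2% baseline, 0.29-0.33 at 3% and 0.29-0.31 at 5%, and a little less if the OGTT displaces a meal. The 95% interval around 0.27 at n = 50 is tanh(0.277 ± 1.96/√47), or about −0.01 to 0.51. At baselines of 2% or more the bias is thus well inside sampling error. This stands as a limit on importance. It does not remove the bias, which has a known direction and can be avoided.

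**Window.** The test lasts 2 hours, and a 3-hour window is a choice. That is fair, and it is listed below as a cost.

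**Conclusion.** The point holds in a conditional and modest form. As written, the plan lets the response to the comparator test into a CGM measure that may be compared with that test, and the bias favors an association. The contribution cannot exceed 0.83 percentage points for the 2-hour test or 1.25 for 3 hours. Whether that matters depends on the threshold and free-living baseline, which the documents leave open. With the two roughly matched, the false-positive rate is moderately raised at low baselines and close to nominal by 3% at 180 mg/dl or 10% at 140 mg/dl. These rates rest wholly on the assumed distributions and curve shape.

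A reader might also infer that every CGM comparison is compromised. The documents do not support that. Mean glucose is barely moved. Nighttime metrics are untouched if the test is done in clinic hours (an assumption). One 2-hour load should matter little for the HbA1c and fructosamine comparisons.

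Severity is low: this is an inexpensive improvement and does not threaten the study.

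**What to change.** Add to the SAP:

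> The clock time of the glucose load will be recorded. For each CGM time-in-range metric compared with the OGTT, readings from the load to 3 h after it will be excluded, and percentages will use the remaining readings as denominator. The full-trace result, and a result excluding the whole OGTT day, will be reported as sensitivity analyses.

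The rule works whatever threshold the sponsor sets and leaves clinical care unchanged.

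Costs:

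- Up to 36 of 2,880 readings (1.25%) are lost per woman, leaving 2,844.
- One clock time must be recorded; no section says that it is now.
- Percentages must be recomputed from a reading-level export. The plan says only that the data "will be downloaded with the Dexcom G7 reader and uploaded to Dexcom CLARITY", but its day/night split already depends on the time of each reading.
- Any response beyond 3 hours, and the fast before the load, stay in the main analysis. The whole-day exclusion checks for both.
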